#### 6.8.1 Efficacy Endpoint:

The primary efficacy endpoint for this study is defined as successful treatment of a bleeding episode at 12 hours after first administration of the study drug. The following are clarification definitions to satisfy regulatory requirements in multiple regions (i.e., the FDA and the EMA).

The primary efficacy endpoint for the FDA is defined as the successful treatment of a mild/moderate bleeding episode at 12 hours after start of treatment. Successful treatment of a mild/moderate bleeding episode is defined as a combination of the following:

- *Good* or *Excellent* response noted by patient/parent/guardian, depending on patient’s age and maturity
- Study drug treatment: No further treatment with study drug beyond timepoint where a Good or Excellent response for this bleeding episode was noted
- No other hemostatic treatment needed for this bleeding episode
- No administration of blood products indicating continuation of bleeding beyond timepoint where a Good or Excellent response for this bleeding episode was noted
- No increase of pain beyond timepoint where a Good or Excellent response for this bleeding episode was noted that cannot be explained other than as continuation of bleeding

The primary efficacy endpoint for the EMA is defined as the proportion of bleeding episodes (mild/moderate and severe combined) with a “good” or “excellent” patient (for mild/moderate bleeding episodes) and physician (for severe bleeding episodes) reported assessment of efficacy at 12 hours after the first administration of study drug.

Secondary efficacy endpoints include:

- Proportion of mild/moderate bleeding episodes successfully treated according to the same criteria as the primary endpoint of efficacy, at all other timepoints
- Proportion of bleeding episodes (mild/moderate and severe, separately and combined) with a “good” or “excellent” patient (and/or physician when available) reported assessment of efficacy at all timepoints
- Time to assessment of a “good” or “excellent” response of the bleeding episodes (mild/moderate and severe, separately and combined) by the patient/parent (and/or physician when available)
- The number of administrations and mean total amount of drug administered per bleeding episode

Tertiary efficacy endpoints include:

- Proportion of bleeding episodes (mild/moderate and severe, separately and combined) with a “good” or “excellent” physician reported assessment of the efficacy at 12 hours (if available)
- Proportion of recurrences (defined as a bleeding episode in the same joint/anatomical location within 24 hours after an initial successful response)
- Proportion of bleeding episodes (mild/moderate and severe, separately and combined) requiring alternative treatment
- Proportion of bleeding episodes (mild/moderate and severe, separately and combined) with successful pain relief

Where applicable, analyses will be done for all patients and by age group aged from birth to <6 years and ≥6 years to <12 years).

## 6.9 Adverse Events Assessments

### 6.9.1 Performing Adverse Events Assessments

An Adverse Event (AE) is defined as any undesirable physical, psychological or behavioral effect experienced by a patient during their participation in an investigational study, in conjunction with the use of a drug or biologic, whether or not product-related. Events that match this description but occur between the time of informed consent and the first administration of the study drug are also regarded AEs, but will be listed as *nonTEAEs*. Disease signs, symptoms, and/or laboratory abnormalities already existing prior to informed consent are not considered AEs, unless they reoccur after the patient has recovered from the pre-existing condition or they represent an exacerbation in severity, duration or frequency.

Bleeding episodes such as in the case of Hemophilia, which are the subject of this study are not regarded AEs. If a bleeding episode was caused by an injury, the injury should not be reported as an AE, unless it resulted in a medical finding other than a bleeding episode (e.g.,

scratch of skin). Therefore, any hemophilia-related events (e.g., hemarthrosis [presenting as swelling, pain, and limited motion], bruising, hemorrhages, or pain at bleeding site) will not be reported as AEs. However, the event may be regarded as an AE if it had occurred in a hemostatically normal patient under the same circumstances.

Hospitalization for the treatment of a bleeding episode regardless of severity, should not be reported as an AE.

All AEs will be recorded in the eCRFs. A description of the event (preferably medical diagnosis, or if no diagnosis is made symptom or sign) including start date/time, resolution date/time, seriousness, severity, relationship to the investigational product, action taken, and outcome should be provided.

All AEs will be followed up until resolution or 30 days after EOS/Termination visit, whichever comes first.

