**Table 1. Classification of severity of bleeding episodes**

Bleeding Episode	Description	Examples
Mild	

• A bleeding that just starts and has little symptoms, i.e., little or no pain, little or no change in the range of motion of affected joint (if joint bleeding event); mild restriction of mobility and activity

	

• Early onset muscle and joint bleeds with no visible symptoms such as little or no change in the range of motion of affected joint (if joint bleeding event); mild restriction of mobility and activity

• Scrapes, superficial cuts, bruises, superficial mouth bleeds and most nose bleeds

Moderate	

• A bleeding that involves swelling or pain including some decrease in range of motion of affected joint (if joint bleeding event) or moderate decrease in mobility and activity

	

• Advanced soft tissue and muscle bleeds into the limbs

• Bleeding into the joint space, such as the elbow, knee, ankle, wrist, shoulder, hip, foot or finger

Severe	

• Severe bleeds are potentially life/limb threatening, produce significant blood loss, pain, or can cause permanent nerve damage

	

• Mouth & neck region – Bleeding from the floor of the mouth, pharynx, or epiglottic area can result in partial or complete airway obstruction.

• Complicated joint bleeds – Hip joint or acetabular hemorrhages

• Iliopsoas hemorrhages

• Bleeding episodes leading to compartment syndrome such as in hand, wrists, forearm and anterior or posterior tibial compartments

• Central nervous system hemorrhages

• Gastrointestinal bleed – bleeding occurs in stomach or intestines

• Acute hemorrhage - such as bleeding into the abdomen

• Bleeding from major trauma

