## 6.9.8 Serious Adverse Events

### 6.9.8.1 Definition

A serious adverse event (SAE) is defined as any AE occurring at any dose that results in death, is life-threatening, requires in-patient hospitalization or prolongation of existing hospitalization, results in persistent or significant disability/incapacity, or is a congenital anomaly/birth defect.

Important medical events that may not result in one of the above may be considered SAEs when, based upon appropriate medical judgment, they may jeopardize the patient and may require medical or surgical intervention to prevent one of the outcomes listed in this definition. Examples of such medical events include allergic bronchospasm requiring intensive treatment in an emergency room or at home, blood dyscrasias or convulsions that do not result in patient hospitalization, or the development of drug dependency or drug abuse. Any suspected transmission via a medicinal product of an infectious agent is also considered an SAE.

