## **9.11 Interim Analysis**

One interim analysis will be performed:

- Upon availability of FVIIa plasma activity data for at least 6 patients in each age group, PK profiles along with all safety and efficacy data available at that time will be reviewed by the DMC. Data will be used to identify any unexpected results that may impact safety or efficacy.
- At the time at least 80 bleeding episodes have been treated, data collected will be reviewed to identify any safety or efficacy issues.

The DMC will review these data and make recommendations to continue the study unaltered, or to make any modifications to the study.

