## 10.8 Data Monitoring Committee

The DMC is responsible for the oversight of patient safety. The DMC will consist of three specialists in the care of hemophilia patients. DMC members will be independent of the study and sponsor. During the course of the trial, the DMC will review efficacy, PK, and/or safety data at a minimum of the following timepoints:

- Each serious adverse drug reaction (i.e., an SAE for which at least a possible, probable, or definite causal relationship is assessed by the investigator and/or the sponsor)
- Quarterly: a concise cumulative listing of all SAEs (regardless of relationship to study drug) that occurred in the study
- After interim analysis specified in Section 9.11

The DMC will make recommendations, as appropriate, for study modification or termination because of concerns over patient safety or issues relating to data monitoring or quality control. This will be submitted in writing to the sponsor's Medical Monitor for consideration and final decision. However, if the DMC at any time determines that a potential serious risk exists to patients in the trial, the DMC Chairperson will immediately notify the Sponsor's Medical Monitor per the DMC Charter.

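### A spontaneous bleed that is fatal, life-threatening or disabling on LR769 need not be reported as an SAE, because the exemption in Section 6.9.1 has no exception based on outcome

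*Protocol*

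**What the plan says.** Protocol Section 6.9.1 sets the rule: "Bleeding episodes such as in the case of Hemophilia, which are the subject of this study are not regarded AEs". It extends this to hemophilia-related events in general, ending the list with "bruising, hemorrhages, or pain at bleeding site) will not be reported as AEs". One exception follows: "However, the event may be regarded as an AE if it had occurred in a hemostatically normal patient under the same circumstances". A separate sentence then deals with admission: "Hospitalization for the treatment of a bleeding episode regardless of severity, should not be reported as an AE".

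Section 6.9.8.1 builds seriousness on top of the AE definition: "A serious adverse event (SAE) is defined as any AE occurring at any dose that results in death, is life-threatening", followed by hospitalization, disability and the other usual criteria.

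The bleeds in scope include dangerous ones. Table 1 says: "Severe bleeds are potentially life/limb threatening, produce significant blood loss, pain, or can cause permanent nerve damage". Its examples include central nervous system, airway and abdominal hemorrhage.

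Section 10.8 gives the DMC each serious adverse drug reaction, a periodic listing ("Quarterly: a concise cumulative listing of all SAEs (regardless of relationship to study drug) that occurred in the study") and the interim data. Section 9.11 defines two interim looks. One comes when FVIIa activity data exist for at least 6 patients in each age group. The other is: "At the time at least 80 bleeding episodes have been treated, data collected will be reviewed to identify any safety or efficacy issues".

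Section 3.1.2.5, and the synopsis with it, adds that if a patient needs surgery, the reason for the procedure is recorded as an AE or SAE where appropriate.

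**The concern.** Exempting ordinary bleeds is sensible. They are the condition under treatment, and counting each one as an AE would swamp the safety tables. The difficulty is that no outcome brings a bleed back into reporting.

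For an investigational hemostatic drug, failure to stop a dangerous bleed is a foreseeable serious harm. The patients are children under 12, the trial is open-label, and safety is a primary objective (Section 2.1). A bleeding death or permanent deficit on treatment is an event the sponsor and the DMC should learn of at once, and a reader of the final report should find it in the SAE table. Under the rule as written, a site could leave it out of safety reporting and still be following the protocol.

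**Working it through.** This is a check of text, and the plan states no figure to reproduce. The steps trace a spontaneous central nervous system bleed, treated with LR769, that ends in death or permanent deficit.

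1. **Is it an AE?** Section 6.9.1 says bleeding episodes under study are not, and that hemorrhages are not reported as AEs. None of its sentences on bleeding is conditioned on outcome.
2. **Does the exception apply?** It asks whether the event would have counted in a hemostatically normal patient in the same circumstances. It turns on circumstances and says only that such an event may be an AE. Bleeding from major trauma, a severe example in Table 1, could qualify. A typical spontaneous hemophilic bleed would not.
3. **Does the surgical route apply?** Only if there is a procedure. A bleed that leads to surgery may be recorded as an (S)AE, while one that kills without surgery has no such route.
4. **Can it be an SAE?** Section 6.9.8.1 requires an AE first. If steps 1 to 3 yield none, there is no SAE.
5. **What depends on that?** The 24-hour report (Section 6.9.8.2), the DMC's per-event and quarterly inputs (Section 10.8), the ad-hoc DMC meeting (Section 6.11, called in case of an SAE) and the tables of AEs, SAEs and TEAEs by regimen (Section 9.8).
6. **What else captures it?** Section 6.8 collects, for each bleed, hospital visit, alternative treatment, pain and time to cessation. It does not list death, sequelae or disability. No efficacy endpoint in Section 6.8.1 records them either.

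Section 6.9.9 offers a contrast: acute allergic reactions and confirmed thrombotic events go on the SAE timeline even when they meet no seriousness criterion. Bleeds with a serious outcome have no matching rule.

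**Reach of the scheduled DMC looks.** The 80 in Section 9.11 counts all treated episodes, whereas the 352 in Section 3.3 is a minimum for mild/moderate episodes alone. The total is therefore at least 352. A look held at exactly 80 covers at most 80/352 = 22.7% of treated bleeds, and severe bleeds lower that share. The text says at least 80, so the look could come somewhat later. The PK look is triggered at 6 of the 12 patients planned per age group. Nothing is scheduled beyond these two looks.

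**Size of the pool.** The documents say only that severe bleeds will be a minority. If they were a share x of all bleeds, 352 mild/moderate bleeds would be accompanied by 352x/(1 − x) severe ones. At an assumed x = 2% this is 352 × 0.02/0.98 = 7.2. At an assumed x = 10% it is 352 × 0.10/0.90 = 39.1. These are severe bleeds treated. They are not serious outcomes missed, a number that cannot be estimated from the documents.

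**The case against.** The strongest reply is that the text is ambiguous and stops short of exempting fatal outcomes. The general AE definition in Section 6.9.1 is broad, and nothing there says a death or deficit after a bleed is exempt. The words on severity qualify only the hospitalization sentence. This stands, and it is why the conclusion is that such a bleed need not be reported. A reader might infer that every bleeding episode is exempt whatever its outcome. The documents do not say so: the exception in Section 6.9.1 and the surgical route both exist, and the treatment of outcome is an inference from silence.

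Uncontrolled bleeds are also not invisible. The proportion needing alternative treatment is a tertiary endpoint, with severe bleeds shown separately (Section 9.7). Severe bleeds are assessed by the physician and enter the EMA primary endpoint. Sites contact parents about weekly (Section 7.3), and investigators must report unanticipated problems to the IRB/IEC (Section 10.2). All this stands, but it records treatment failure or informs the ethics committee. It does not put a death or disability before the sponsor and the DMC as a safety event.

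Three further inferences are tempting and unsupported:

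- That the DMC would never see such a bleed. It reviews efficacy data at the Section 9.11 looks, the list in Section 10.8 is a minimum, and the DMC Charter is not among the documents.
- That a neutralizing antibody would go unnoticed. Samples are taken at every scheduled follow-up visit, and the stopping rule is triggered by the antibody itself.
- That the safety conclusion is shown to favor the drug. Failures count against efficacy, and only an addendum to the SAP is available, so how the main SAP tabulates deaths cannot be checked.

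**Conclusion.** The gap is real and narrow. As Sections 6.9.1, 6.9.8.1, 9.8 and 10.8 stand together, a spontaneous hemophilic bleed that is fatal, life-threatening as it occurs or disabling during LR769 treatment can be left out of SAE reporting, the DMC's SAE reviews and the SAE tables without breaking any stated rule. It would remain in the efficacy data, where no listed item or endpoint records death or disability, and where the last look tied to episode count comes at 80 or more treated bleeds.

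The number of such events is unknown and probably small. The conclusion depends on no assumed rate. It rests on reading the specific sentences about bleeds as overriding the general AE definition, and on the Charter and main SAP not already closing the gap.

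**What to change.** Reconcile Section 6.9.1 with Sections 6.9.8.1, 9.8 and 10.8:

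- Keep the exemption for bleeds with a non-serious course and for hospitalization solely to treat them.
- State that a bleed or its complication is reported under Section 6.9.8.2 if it results in death, is life-threatening as it occurs, or leaves persistent or significant disability.
- Include these events in the DMC's per-event and quarterly listings in Section 10.8, and tabulate them by regimen in Section 9.8.

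The change should not reach every severe bleed in which LR769 was stopped for insufficient effect. That alone meets no criterion in Section 6.9.8.1 and is already captured as an efficacy outcome.

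The cost is a few sentences, a few extra SAE reports and a slightly less favorable SAE table. No visits are added, and clinical management does not change.

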### 6.9.2 Timing

Adverse events will be collected from the time of signing of the informed consent until completion of the study. At each study visit the patient/parent will be asked to report any and all changes in health status or condition (AEs) experienced since the previous visit.

Additionally, the patient/parent will be asked specifically whether the patient experienced any signs and symptoms that may indicate a thromboembolic event occurred. These may include, among others, headache, shortness of breath, chest pain, cyanosis, calf pain, swelling/edema, redness, venous distension or pain on dorsiflexion of the foot.

### 6.9.3 Severity

Adverse events will be graded by the investigator according to severity:

- Mild: Symptom(s) barely noticeable to the patient and/or does not make the patient uncomfortable. The AE does not influence daily performance or functioning. Medical intervention is not ordinarily needed for relief of symptom(s).
- Moderate: Symptom(s) of a sufficient severity to make the patient uncomfortable. Performance of daily activities is influenced. Treatment of symptom(s) may be needed.
- Severe: Symptom(s) of a sufficient severity to cause the patient severe discomfort, and/or result in a marked impairment of function or may be even life-threatening. Severity may cause cessation of treatment with the study drug. Treatment for symptom(s) is given. The AE produces sequelae, which may also require (prolonged) treatment.

*Note: Severe is not equivalent to serious.*

#### 6.9.4 Relationship

For all AEs, the Investigator will be asked to record the drug relatedness of the event in the source documents and enter the data in the eCRF. For this assessment the investigator will need to take into account the time relationship between drug administration and the occurrence of the event, the expected pharmacology of the study drug, the potential contribution of the underlying disease under investigation and/or any other concomitant diseases/medical history, evolution of the event when the drug was withdrawn and whether the event re-occurred after a re-challenge.

The relationship criteria include:

- *unrelated* (event with a time to drug intake that makes a relationship unlikely and disease or other drugs provide a clear explanation, negative re-challenge)
- *remote/unlikely* (event with a time to drug that makes a relationship improbable (but not impossible) and disease or other drugs provide plausible explanations)
- *possibly* (event with reasonable time relationship to drug intake that could also be explained by disease or other drugs and information on drug withdrawal/re-challenge lacking or unclear)
- *probably* (event occurred within reasonable time relationship to drug intake, is unlikely to be attributed to disease or other drugs and response to withdrawal)
- *definitely* (event with plausible time relationship to drug intake which cannot be explained by disease or other drugs and/or plausible response to withdrawal and/or definitively pharmacologically plausible and/or positive re-challenge).

#### 6.9.5 Expectedness

An AE is expected if the nature, severity and outcome of the event are consistent with the reference safety information, i.e., the Investigator's Brochure.

#### 6.9.6 Clinical Significance

Clinical significance is defined as any variation in physical/laboratory findings that has medical consequences that result in an alteration in the patient's medical care.

#### 6.9.7 Clinical Laboratory Adverse Events

Any change in laboratory value outside the normal range will be regarded an AE if the investigator assesses the value as clinically significant. Changes in coagulation parameters expected in hemophilia patients are not regarded as AEs, unless they lead to clinical measures to prevent or treat any untoward events associated with the deviation of the parameter.

## 6.9.8 Serious Adverse Events

### 6.9.8.1 Definition

A serious adverse event (SAE) is defined as any AE occurring at any dose that results in death, is life-threatening, requires in-patient hospitalization or prolongation of existing hospitalization, results in persistent or significant disability/incapacity, or is a congenital anomaly/birth defect.

Important medical events that may not result in one of the above may be considered SAEs when, based upon appropriate medical judgment, they may jeopardize the patient and may require medical or surgical intervention to prevent one of the outcomes listed in this definition. Examples of such medical events include allergic bronchospasm requiring intensive treatment in an emergency room or at home, blood dyscrasias or convulsions that do not result in patient hospitalization, or the development of drug dependency or drug abuse. Any suspected transmission via a medicinal product of an infectious agent is also considered an SAE.

### 6.9.8.2 Reporting Serious Adverse Events

The necessity and time requirements for reporting of SAEs to the Sponsor or designee and regulatory agencies are as follows:

- All SAEs will be reported via the eCRF system within 24 hours of the Investigator's first knowledge of the event, even if the event does not appear to be related to the study drug. If reporting via the eCRF is not available, the SAE may be recorded on the SAE form and reported via fax in order to meet the reporting requirements.

**In case of failure of the eCRF reporting, SAE forms are to be directed to:**

[contact] (country-specific fax instructions will be provided where applicable)

- For all SAEs, a detailed written description that includes copies of available relevant patient records, autopsy reports, and other documents will be sent within 24 hours of the Investigator's first knowledge of the SAE.
- SAEs that are life threatening or result in death, and are unexpected and related to study drug will be reported to regulatory authorities within 7 days of receipt of the event. Any follow up to the initial SAE report will be submitted to regulatory authorities within 8 days of the initial report (ie, 15 days of receipt of the initial report).
- Any SAE that is unexpected and related to study drug, results in hospitalization or prolongs an existing hospitalization, results in persistent or significant disability/incapacity, or is a congenital anomaly/birth defect will be reported to regulatory authorities within 15 days of receipt of the report. Some regulatory authorities may have

alternative timelines for submission of suspected unexpected serious adverse reactions. In those cases, specific local requirements for submission of SAE reports will be applied.

- All SAEs will be followed until resolution or stabilization. Follow-up reports for SAEs reported as 7- or 15-day reports will be submitted within the same time frame as the initial report.

Additionally, the Institutional Review Board (IRB) and/or Ethics Committee (EC) must be notified in writing of any unexpected, related SAEs or as required by the local IRB/EC. It is the responsibility of the Investigator to notify the IRB/EC.

If applicable, SAEs will be reported to the appropriate regulatory agencies by the Sponsor. In case the local regulations require notification through the investigator, the Sponsor will facilitate this process.

Any SAEs ongoing at the time of study termination will be followed until resolution or stabilization, with a maximum of 30 days after last study drug administration. Any SAE occurring within 30 days of the last dose of study drug will be reported even if the SAE occurs after the study has ended.

